5.1.2. Part B

Optional Part B of the study is an open-label, non-randomised up to 7-period fixed sequence study design to evaluate the selected MR prototype coated tablet formulation(s) at different tablet strengths or as multiple unit doses and with or without apertures in the tablet coatings (Figure 2). Up to 4 different MR prototype coated tablet formulations may be selected for investigation in Part B. These will be selected from Part A and ongoing interim reviews in Part B; the selected formulations may be adjusted during interim reviews in Part B. The tablet strengths and the number of dosing units selected in Part B will be based on the exposure of GSK2982772 achieved in an ongoing high dose PK study in which doses of the IR tablet up to 240 mg TID are being administered, and the bioavailability of the selected MR prototype coated tablet formulations relative to the IR tablet (from Part A). Up to 4 different dose levels (as different tablet strengths or multiple unit doses) may be administered in Part B. The proposed dose levels are 120 mg, 480 mg, 960 mg and 1200 mg but these may be adjusted following review of the data from Part A or following the interim reviews during Part B, as appropriate. In Part B, administration of the MR prototype coated tablet formulations will either be in the fed or fasted state, or administered 30 or 60 minutes before a standard or high-fat (Period 7 only) breakfast/evening meal (Period 7 only), which will be based on emerging PK data. There will be an interim review following each of Periods 1 to 5 of Part B to select the dose level, formulation and prandial status, as appropriate, for each subsequent period. An interim data review after Part B Period 6 will determine if optional Period 7 is required and the dose level, dosing time (morning or evening), formulation and prandial status for that period.

Participants will be admitted to the clinic in the morning of the day before dosing (i.e., Day -1) of each inpatient period. Each inpatient period will consist of a 4-day, 3-night

inpatient period with a minimum of 7 days washout between doses. A follow-up visit will occur at 7 to 9 days after the last study treatment.
*

CONFIDENTIAL

Interim decisions based on PK and safety data. Periods 2 to 7 are flexible and the dosing regimen will be dependent on the outcome of the preceding periods.

¹ Proposed dose levels that may be adjusted following review of the data from Part A

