Interim decisions will only be made after a complete review of all relevant data collected from the previous dose group. Data should be available from a minimum of 12 participants who have completed the planned safety and PK assessments up to 24 hours after dosing, or 48 hours after dosing for the food effect assessment and for Part B; if full data, as described below, are not available for 12 participants, the PI, scientific lead and sponsor will take a decision as to whether the data available are sufficient to support the formulation selection decision. An evaluable participant must also have received the relevant test and reference formulations for the comparisons of interest e.g., an MR formulation and the IR reference and/or the selected MR formulation in both the fed and fasted states. If data in fewer than 12 participants are used in the decision process, replacement participants will not be dosed with previous regimens to increase the number of participants in the completed regimen.

The following data will be provided to the sponsor by Quotient Sciences:

- AEs, vital signs, ECGs, safety laboratory data and physical examinations.
- Plasma concentrations of GSK2982772.

- PK parameter estimates GSK2982772 AUC_(0-inf), AUC_(0-t), AUC₍₀₋₂₄₎, T_{lag}, T_{max}, C_{max}, C_{24h}, (C_{12h} for IR only) t_{1/2}, Frel based on AUC and C_{max} for test vs reference formulations and fed vs fasted, where relevant (Part A).
- PK parameter estimates GSK2982772 AUC_(0-inf), AUC_(0-t), AUC₍₀₋₂₄₎, T_{max}, C_{max}, C_{24h}, t_{1/2} (Part B).
- Protocol deviations will be reviewed to ensure they have had no significant impact on the above data

The decision on formulation, tablet strength, dose level, dosing time (Part B Period 7 only) and prandial state selection or stopping the study will be made by the Quotient study team (i.e., PI, scientific lead and pharmacokineticist) and sponsor study team (as a minimum the sponsor's medical monitor, Clinical Pharmacokinetics Modelling and Simulation [CPMS] and Global Clinical Safety and Pharmacovigilance [GCSP]). The decision will be documented and signed by the PI as per Quotient Sciences current standard operating procedure (SOP). Evidence of the decision will be retained in the Investigator Site File (ISF) and GlaxoSmithKline (GSK) Trial Master File.

The following decision criteria will be used as a guide to MR formulation selection during the study.

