Since the aim of the MR development programme in to provide a QD formulation with as high as possible C_{min} , the decision criteria will be based on this PK parameter. To avoid issues with potential outliers at a single nominal time point (e.g. defining C_{24h} as minimum observed concentration $[C_{min}]$), the decision criteria will be based on the nominal PK sampling times between 18 and 24 hours. Other PK parameters may also be taken into consideration in the MR formulation selection including, but not limited, to bioavailability relative to IR, ratios of $C_{max}:C_{18h}$, $C_{max}:C_{20h}$, $C_{max}:C_{22h}$ and $C_{max}:C_{24h}$ and between subject coefficient of variation (CVb) of C_{18h} , C_{20h} , C_{22h} and C_{24h} . The duration of drug release may also be taken into consideration since shorter drug release durations using weaker polymers may be more susceptible to food effect whereas longer release duration will be more susceptible to PK variability due to inter- and intra-subject differences in gastrointestinal transit time.

Food effect arm/s may be conducted with one or more MR formulations and/or one or more fed states.

N.B. The release rate of MR1 is planned to be similar to the slowest release minitab in study 205017 (~12h for 80% release) and the release rate of MR2 will be the slowest available within the design space.

2019N407804_00 209261

Decision Criteria for Part 1: Period 5

If an intermediate release rate (MR3) is evaluated in Period 4, then a 2nd intermediate release rate (MR4) between MR3 and either MR1 or MR2 may be evaluated using the same criteria as in Period 4. If the criteria for evaluating an intermediate release rate in Period 5 are not met, then either MR1, MR2 or MR3 will be administered with a high-fat meal in Period 5.

If a faster release rate than MR1 is evaluated in Period 4, then an even faster release rate or an interim release rate between MR3 and MR1 or MR2 may be evaluated based on the same criteria as Period 4. If the criteria for evaluating an even faster release rate on an intermediate release rate in Period 5 are not met, then either MR1 or MR3 will be administered with a high-fat meal in Period 5.

Decision on which MR Formulation to be used for assessment of High-Fat Meal: Periods 4, 5 and/or 6

The MR formulation to be selected for the food effect arm will ideally have the highest GSK2982772 concentrations in the majority of timepoints between C_{18h} and C_{24h} along with the lowest CV_b .

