Decision on which MR Formulation to be taken to Part 2

The duration of release for the 120 mg and 480 mg MRX formulations in Periods 1 and 2 will have a similar release rate duration as the optimal MRX formulation from Part A, where optimal is defined in the same way as for the food effect arm (e.g. the highest GSK2982772 concentrations in the majority of timepoints between C_{18h} and C_{24h} along with the lowest $CV_{b)}$.

Decision of whether to evaluate 480 mg or 120 mg MR_{Yh} in Part B

If dose normalised C_{min} is $\geq 10\%$ different compared to the 240 mg dose normalised C_{min} ,

then the MR release duration may be adjusted in Period 3 and/or Period 4.

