- The specific formula that will be used to determine eligibility and discontinuation for an individual participant should be determined prior to initiation of the study. In other words, several different formulae cannot be used to calculate the QTc for

an individual participant and the lowest QTc value used to include or discontinue the participant from the trial.

• For purposes of data analysis, QTcB, QTcF, another QTc correction formula or a composite of available values of QTc will be used as specified in the Reporting and Analysis Plan.

Prior/Concomitant Therapy

- 16. Past or intended use of over-the-counter or prescription medication including herbal medications within 7 days prior to dosing (paracetamol/acetaminophen [up to 2 g per day], hormone replacement therapy and hormonal contraception are permitted).
- 17. Live or attenuated vaccine(s) within 30 days of enrolment, or plans to receive such vaccines during the study or plans to receive a vaccine within 30 days + 5 half-lives of the last dose of study medication.

Prior/Concurrent Clinical Study Experience

- 18. Participation in the study would result in loss of blood or blood products in excess of 500 mL within a 56 day period; therefore donation or loss of greater than 400 mL of blood within the previous 3 months.
- 19. Exposure to more than 4 new chemical entities within 12 months prior to the first dosing day.
- 20. Current enrolment or past participation within the last 3 months before signing of consent in this or any other clinical study involving an investigational study treatment or any other type of medical research.
- 21. Participants who have previously been enrolled in this study. Participants in Part A of this study are not permitted to participate in Part B.

Diagnostic assessments

- Current or history of renal disease or estimated glomerular filtration rate by Chronic Kidney Disease Epidemiology Collaboration (CKD-EPI) equation calculation <60 mL/min/1.73m² at screening.
- 23. Presence of Hepatitis B surface antigen (HBsAg) at screening. Positive Hepatitis C antibody test result at screening or within 3 months prior to first dose. As potential for and magnitude of immunosuppression with this compound is unknown, participants with presence of hepatitis B core antibody (HBcAb) should be excluded. Participants positive for HBsAg and/or positive for anti-HBc antibody (regardless of anti-HBs antibody status) are excluded.

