7.1.2. Treatments Administered - Part B

Regimen	G	Н	I (Optional)	J (Optional)	K (Optional)	L	M (Optional)
Study Treatment Name:	GSK2982772	GSK2982772	GSK2982772	GSK2982772	GSK2982772	GSK2982772	GSK2982772
Dosage formulation:	MR prototype Coated Tablet MRX	MR prototype Coated Tablet MRX	MR prototype Coated Tablet MRX or MRX1	MR prototype Coated Tablet MRX or MRX1	MR prototype Coated Tablet MRX, MRX1 or MRX2	MR prototype Coated Tablet MRX, MRX1 or MRX2	MR prototype Coated Tablet MRX, MRX1 or MRX2
Unit dose strength(s)/ Dosage level(s):	120 mg / 120 mg (may be changed following review of Part A data)	tbc / tbc					
Route of Administration	Oral with 240 mL water						
Dosing instructions:	1 tablet, on the morning of Day 1 Food status: tbc	xx tablets, on the morning of Day 1 Food status: tbc	xx tablets, on the morning of Day 1 Food status: tbc	xx tablets, on the morning of Day 1 Food status: tbc	xx tablets, on the morning of Day 1 Food status: tbc	xx tablets, on the morning of Day 1 Food status: tbc	xx tablets, on the morning OR evening of Day 1 Food status: tbc

Regimen	G	Н	I (Optional)	J (Optional)	K (Optional)	L	M (Optional)
Packaging and Labelling	100 cc HDPE white bottle labelled as required per country requirement.						
Manufacturer	Quotient	Quotient	Quotient	Quotient	Quotient	Quotient	Quotient

MRX is the formulation selected from Part A. MRX1 and MRX2 are alternative MR formulations that may be investigated from Part A. Tablets in Periods 1 and 2 will be manufactured with apertures. Tablets may be manufactured with or without apertures (i.e., drilled or non-drilled) from Period 3 onwards. Tablets without apertures will be manufactured based on a formulation which has already been dosed.

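### Does the Part B 10% trough guide need the within-participant 480 mg/120 mg ratio as a second condition?

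*Protocol*

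**What the plan says.** Protocol 5.1.3 plans that "the 120 mg and 480 mg MRX formulations in Periods 1 and 2 will have a similar release rate duration" as the best Part A formulation. If the dose-normalised Cmin of a strength is at least 10% "different compared to the 240 mg dose normalised" Cmin, "then the MR release duration may be adjusted in Period 3 and/or Period 4".

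The 240 mg reference has to come from Part A. In Protocol 5.1.2, "The proposed dose levels are 120 mg, 480 mg, 960 mg and 1200 mg but these may be adjusted", so 240 mg is not a proposed Part B level. Under Protocol 6.2, "Participants in Part A of this study are not permitted to participate in Part B".

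Three statements set the weight of the condition. Protocol 5.1.3 introduces the list with "The following decision criteria will be used as a guide to MR formulation selection during the study". It also says that, to avoid reliance on one time point, "the decision criteria will be based on the nominal PK sampling times between 18 and 24 hours". Other PK parameters may be considered, and decisions follow a complete review of the relevant data. The Synopsis and Protocol 5.4 give the aim: polymer ratios may be changed if one or both alternative strengths depart from the optimal 240 mg profile.

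**The concern.** The comparison is unpaired, and its cut-off is well inside the noise for concentrations at 18 to 24 hours. The 120/240 and 480/240 ratios also share the same Part A mean and the same Part B cohort, so their errors move together. If the Part B cohort happens to run low or high, both strengths tend to cross 10% in the same direction, and that can look like replication. A strength effect that runs with dose would push the two strengths apart, yet the condition treats both patterns alike.

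As planned, 120 mg and 480 mg are given to the same people in Periods 1 and 2. Their ratio is free of the cohort difference, but the condition does not name it. At stake is one or two Part B periods spent on a changed release duration when only the cohorts differ.

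**Working it through.** **Inputs.** From Protocol 10.2: between-subject CV 65.1% (C22h, the lowest of the four trough times) to 73.2% (C24h, the highest), with within-subject CV 40.4% and 44.9%. From Protocol 5.1.3: at least 12 participants. Log-scale variance is ln(1 + CV²). The between-subject CV is read as total single-period variability.

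- C22h: σT² = 0.3533, σW² = 0.1512
- C24h: σT² = 0.4291, σW² = 0.1837

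**Check against the plan's own figures.** (3/7) × 0.4291 = 0.1839, which gives a within-subject CV of 44.9%, as stated. The 90% CI half-width for C24h at N=12 is exp(1.796 × √(2 × 0.1837/12)) − 1 = 36.9%, against 36.2% in Table 3. The inputs are read correctly.

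**Chance crossing for one strength.** The log ratio to 240 mg has variance 2σT²/n, so SE = 0.243 (C22h) and 0.267 (C24h). The cut-offs are ln 0.9 = −0.105 and ln 1.1 = 0.095. With no true difference:

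- C22h: 0.332 + 0.347 = 0.679
- C24h: 0.347 + 0.361 = 0.708

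**Both strengths.** The correlation of the two ratios is 1 − σW²/(2σT²) = 1 − 0.428/2 = 0.786. The bivariate normal gives:

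- both cross in the same direction: 0.485 / 0.510
- they cross in opposite directions: 0.027 / 0.034
- at least one crosses: 0.847 / 0.871

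**Sensitivity.**

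- 16 per part: one strength 0.633 / 0.665, same direction 0.445 / 0.472.
- Assumed CV of 40%, 12 per part: 0.524 and 0.352.
- CV read as between-subject only, 12 per part: 0.729 / 0.754 and 0.563 / 0.586.
- Log-mean of C18h to C24h with assumed correlation 0.5 to 0.9: one strength 0.618 to 0.682.

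**What a required paired condition would do.** The log of the 480/120 ratio has SE √(2σW²/n) = 0.159 / 0.175. With no true difference it is itself at least 10% off in 0.528 / 0.566 of trials. Suppose adjustment required the ratio to 240 mg and the paired ratio both to cross in the same direction. With no true difference, a given strength is then flagged 0.262 / 0.287 of the time, and at least one strength 0.497 / 0.541. The probability that 480 mg is flagged low (12 per part, C22h / C24h) is:

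| True state | Ratio to 240 mg alone | Paired ratio also required |
|---|---|---|
| No difference | 0.332 / 0.347 | 0.124 / 0.137 |
| 480 mg 20% low, 120 mg 25% high | 0.69 / 0.67 | 0.68 / 0.66 |
| Only 480 mg 20% low | 0.69 / 0.67 | 0.57 / 0.54 |
| Both 20% low | 0.69 / 0.67 | 0.21 / 0.22 |

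In the last row, at least one strength is flagged, in either direction, about 49-54% of the time. That is no different from the 50-54% when nothing is wrong. The likelihood ratio for a low flag falls from 0.69/0.332 = 2.1 and 0.67/0.347 = 1.9 to 0.209/0.124 = 1.7 and 0.222/0.137 = 1.6.

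**Was the paired ratio available?** Protocol 7.1.2 leaves the dose of the second Part B regimen and the food status of every Part B regimen to be confirmed. The display descriptions in SAP 5.1 give G as 480 mg fasted, H as 960 mg fasted and 120 mg fasted only at K. If G and H are Periods 1 and 2, there was no 480/120 ratio before Period 3. All Part B labels there are MR-16h, so no change of release duration is recorded.

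**The case for a change.** The best case for a change is this. The 10% figure is the only numerical trigger in this part of 5.1.3, and an open list of other parameters does not repair it. The same section says an evaluable participant must have received both test and reference for the comparison of interest. Under the proposed doses nobody can meet that for 120/240 or 480/240, while everyone given both Part B strengths meets it for 480/120. SAP 8.1.5.1 already lists 480 mg versus 120 mg as a dose-effect contrast. The remedy would take a few sentences and no extra samples. For an effect that runs with dose it costs almost no detection, and it cuts wrong-direction flags for 480 mg from 9-12% to under 0.1%.

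The description of the noise stands, and so does the point that two strengths crossing together is not independent confirmation. The remedy does not follow. Its good performance belongs to one pattern of truth. "MRX is the formulation selected from Part A", and the alternative strengths are meant to match that formulation's 240 mg profile, so a shift common to both strengths is something the team needs to see. Such a shift is plausible, because Protocol 7.1.1 and 7.1.2 name different manufacturers for the two parts. A check of in vitro dissolution, offered to cover that case, would have no criterion of its own. The remedy also keeps the 10% cut-off that causes most of the false crossings: even a paired comparison with 240 mg would cross 53-57% of the time by chance.

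**Conclusion.** No change to the plan. The 10% condition is a weak signal: with 12 per part and no true difference it is met for a given strength about 68-71% of the time, and for both strengths in the same direction about 49-51%. These figures assume that the largest variability seen in the earlier minitab study applies here; at an assumed CV of 40% they are 52% and 35%. They are also probabilities that a condition is met, not that a tablet is changed. The wording is permissive, the part is optional, its strength objectives are exploratory, and Protocol 10.1 tests no formal hypothesis.

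Making the paired ratio compulsory is a trade-off with no clear gain. It lowers chance crossings for a given strength to 26-29%, but lowers detection from 67-69% to 54-57% when only 480 mg is 20% low, and to 21-22% when both are. It would also have been impossible to evaluate on the regimen order the SAP suggests. The amendment history already refers to review of Part B Periods 1 and 2, so a rewritten Period 3 criterion would have little left to govern. The plasma concentrations reach the review team, and Protocol 5.1.3 lets it consider other parameters. A pharmacokineticist can therefore set the within-participant ratio, with its interval, beside the comparison with 240 mg whenever two strengths share a prandial state. The protocol as written allows that.

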5.2. Number of Participants

It is planned to enrol up to 16 participants into each part of the study to allow for sufficient data in at least 12 evaluable participants. For Part A, an evaluable participant will have received the IR tablet formulation (reference) and at least one of the MR formulations and will have completed the planned safety and PK assessments up to 24 hours after dosing. For the food effect assessment, an evaluable subject will have received the chosen MR formulation in the fasted state and the relevant prandial state and will have completed the planned safety and PK assessments up to 48 hours after dosing. For Part B, an evaluable participant will have completed the planned safety and PK assessments up to 48 hours after dosing with at least one MR prototype coated tablet formulation.

Participants withdrawn due to an IMP-related AE that is at least moderate in severity or termination of the study will not be replaced. If participants prematurely discontinue the study for other reasons, additional replacement participants may be recruited at the discretion of the Sponsor in consultation with the investigator.

Up to 4 replacement participants may be enrolled in each part of the study. The maximum number of participants that may be dosed in each part of the study is 20.

Replacement participants enrolled will be dosed with the next planned treatment of the withdrawn participant, and they will not receive any treatment that the withdrawn participant has already received unless required to obtain the minimum number of evaluable participants required for interim decisions, and to obtain data in any other treatment that is required for a valid comparison. Replacement participants will receive the required treatments in the same order as planned for the original participants and the minimum washout period will be respected with regard to the timing of dosing.

5.3. Participant and Study Completion

A participant is considered to have completed the study if he/she has completed all phases of the study including the last scheduled procedure shown in the SoA i.e., the follow-up visit.

The definition of the end of the study is defined as the point at which the sponsor determines that any remaining optional groups are not required to meet the objectives of the trial i.e., signed dose decision document. If all optional groups are used, completion of the last follow-up visit will be considered the end of the study.

5.4. Scientific Rationale for Study Design

Previous clinical studies of IR formulations of GSK2982772 resulted in a high peak:trough ratio of GSK2982772. Additionally, the short half-life for GSK2982772 (~2 to 3 hours) necessitates BID or TID dosing of an IR formulation. As a result, MR formulations using a polymer matrix approach with minitablets in capsule and MR tablet

formulations were investigated. The emerging PK data of the MR formulations investigated to date have demonstrated that a OD PK profile can be achieved in the fasted state but the polymer matrix formulation is susceptible to food effects when administered with a high-fat breakfast. The purpose of this study is to evaluate MR prototype coated tablet formulations. The MR prototype coated tablet formulation uses a combination of a controlled-release polymer matrix and controlled-release coating to achieve a modified-release of the drug. The MR tablet coating used in Part A and the initial periods of Part B will have an aperture drilled into the enteric coating of either side of the tablet. This allows some drug release to commence in the stomach whilst providing controlled release throughout the GI tract. This MR tablet coating has been used in other formulations (e.g. Lamictal XR) and in vivo has shown robustness against food effects. The HPMC polymer has been shown to be effective in achieving a controlled delay to the drug release rate and thus lowering C_{max} and increasing the C_{24h} of the product. However, it is believed that the digestive mechanical action that the dosage form is exposed to in the fed stomach, and/or the longer stomach retention time when dosed in the fasted state, causes an increase in the rate of drug release. Application of an enteric coating with apertures will control the release rate when in the stomach. In Part B only, a new IMP will be manufactured to allow comparison of the tablet coating either with apertures (i.e., drilled) or without apertures (i.e., full coat/non-drilled).

Part A of the study is an adaptive crossover study that will optimise the MR prototype coated tablet formulation to provide a formulation suitable for QD dosing and has no clinically significant food effect. The MR prototype coated tablet formulations have a matrix core containing hypromellose polymers. The MR prototype coated tablet formulations will be optimised within a one-dimensional design space where release rate from the tablet will be adjusted by varying the polymer ratio in the tablet core. The polymers will be hypromellose 2208 K3LV (polymer 1) and/or K100LV (polymer 2) and/or K4M (polymer 3). The dose will be fixed at 240 mg, and the in vitro release rate will be targeted such that the tablet core of GSK2982772 MR prototype coated tablet formulation MR1 will have a dissolution profile that is similar to the release rate of the slowest release MR minitab formulation from Study 205017 (approximately 80% in vitro release at 12 hours). GSK2982772 MR prototype coated tablet formulation MR2 will be designed such that the in vitro dissolution is slower than that of MR1, and will be the slowest available within the design space. If neither MR1 nor MR2 provide an optimal profile, further MR prototype coated tablet formulations will be investigated. The impact of food on the pharmacokinetics of GSK2982772 will also be evaluated for the selected formulation(s). After completion of Periods 3, 4 and 5, interim analyses will be conducted to determine the formulation and prandial status to be investigated in the next period. After completion of Part A, an interim analysis will be conducted to identify MR prototype coated tablet formulations for progression into Part B. If none of the MR prototype coated tablet formulations are suitable, then Part B of the study may not be conducted or Part B may be used to continue to optimise the MR prototype coated tablet formulations, which may include varying the tablet coating either with apertures (i.e. drilled) or without apertures (i.e., full coat/non-drilled) by the manufacture of a new IMP.

Optional Part B will assess the pharmacokinetics of alternative tablet strengths (120 mg and 480 mg, or alternative strengths) as allowed by the design space or tablets with apertures (i.e., drilled) or without apertures (i.e., full coat/non-drilled) or multiple dosing

units of the optimum MR formulation selected from Part A. If the in-vivo profile of either or both the 120 mg or 240 mg tablets (or alternative strengths) differs from the optimal profile with the 240 mg, the ratio of the polymers K3LV, K100LV and/or K4M may be adjusted within each of the alternative strengths. In order to assess the effect of the aperture on the in vivo performance of the formulation, a fully coated tablet (i.e., without apertures) may be assessed in Part B, Period 3 onwards. If fully coated tablet(s) are dosed, the core composition will match a previously dosed formulation to allow a valid comparison. To investigate whether the between-subject variability in absorption time observed following administration of 480 mg tablet with a high-fat breakfast (administered in previous periods) can be reduced; a change to the food regimen or time of administration may be explored in Part B, Period 7. Subjects may be dosed in the fasted state or fed state (standard or high-fat breakfast/evening meal) or in the fasted state followed by a delayed standard or high-fat breakfast/evening meal, on the morning or evening of Day 1. Prior to initiation of Part B, a substantial amendment to the investigational medicinal product dossier (IMPD), will be submitted to the MHRA for approval, to include updated information on the selected GSK2982772 MR prototype coated tablet formulations at alternative strengths.

As this is a Phase 1 study, the most relevant population is healthy participants which allows characterisation of safety, tolerability and PK in a homogenous population without potential biases from a patient population. The European Medicines Agency (EMA) recommends including participants aged 18 years and older with normal weight, who are non-smokers, without a history of alcohol or drug abuse. The latter criteria are proposed to avoid interaction on drug metabolism and to avoid non-compliance. Therefore, this study will enrol healthy male and female participants aged between 18 to 65 years of age.

